# • Not related:

Any AE/SAE that is considered to be 'Definitely Related', 'Probably Related', or 'Possibly Related' to the IMP will be deemed an AR or SAR (and, if unexpected, a potential SUSAR) for onward reporting purposes. Only events that are considered to be 'Not Related' to the IMP will be deemed AEs or SAEs

Where non Investigational Medicinal Products (NIMPs) and the AE is considered to be related to an interaction between the IMP and the NIMP, or where the AE might be linked to either the IMP or the NIMP but cannot be clearly attributed to either one of these, the event will be considered as an AR. Alternative causes such as natural history of the underlying disease, other risk factors and the temporal relationship of the event to the treatment should be considered and investigated. The blind should not be broken for the purpose of making this assessment.

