Secondary Endpoints	
 
Number of eligible women who are recruited into the study.
 
Proportion of pregnant women presenting at or before 28 weeks gestation [when the intervention will be started].
 
Adherence to therapy (ascertained by review of diary and returned study medication)
 
Proportion of women in the placebo group and proportion of those in the active group (if tested prior to starting metformin) who have gestational diabetes at 24-30 weeks
 
Ability to measure key clinical variables:
 
Proportion of women who are recruited but then lost to follow up for the primary and secondary outcomes.
 
Identify an appropriate method by which we can identify women and avoid double randomisation to address co-enrolment (i.e. GPS home identifiers, thumb or finger print).
 
Adverse events in each group
 
					

IMP(s)	(s) Metformin or placebo					
IMP Route of Administration	Oral					
NIMP(s)	N/A					
	This is a feasibility study of a randomised clinical trial of metformin (compared with matched placebo) for the prevention of gestational diabetes and pregnancy hypertensive disorders in obese pregnant women. This study will help to determine whether we can recruit enough women to conduct a larger trial in the future, to measure if the routine administration of metformin could prevent gestational diabetes and pregnancy hypertensive disorders in obese pregnant women in resource poor settings (in Malawi and Zambia).					
Lay Summary of Trial	Gestational diabetes (too much sugar in the blood in pregnancy) and pregnancy hypertensive disorders (high blood pressure that occurs in pregnancy) both cause maternal and neonatal deaths and long term problems. Gestational diabetes with an estimated global prevalence of 16% (with higher rates in in South Asia and Africa) increases the incidence of the adverse pregnancy outcomes. If left untreated it also increases the risk of future obesity and diabetes. Pregnancy hypertensive disorders account for 17.3% of maternal deaths in low income countries, and are the second commonest cause of maternal death after haemorrhage (severe loss of blood).					

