### 9. STUDY ASSESSMENTS

#### 9.1 SAFETY ASSESSMENTS

Safety will be assessed at each routine clinic visit and documented in the medical notes and eCRF. Serious Adverse Events (SAE) will be reported as described in section 12. However, the most common adverse reactions known to be caused by metformin are: nausea, vomiting, diarrhoea, abdominal pain and loss of appetite: most resolve spontaneously. We will record on the eCRF and reported as AE's any of these symptoms that have been experienced during the seven day period, preceding the study visit. Interim un-blinded outcome data will be made available to the Data Safety and Monitoring Committee (DSMC).

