# 12. PHARMACOVIGILANCE

The Investigator is responsible for the detection and documentation of events meeting the criteria and definitions detailed below.

Full details of contraindications and side effects that have been reported following administration of the IMP can be found in the relevant Summary of Product Characteristics (SPC). A specific version (by date) of the SPC will be identified as the source of the RSI, and will be submitted to the PMPB for that purpose.

Participants will be advised to contact their Investigator at any time after consenting to join the trial if any symptoms develop; alternatively participants will be able to report symptoms at their monthly clinic visit. All Serious Adverse Events (SAE) that occur after informed consent until 28 days after delivery of the baby must be recorded and submitted to the regulatory authorities (PMPB) and trial sponsors as soon as possible (within 24-48 hours) after the site becomes aware of the event. In the case of a common AE (known to be caused by Metformin and documented in the SPC) a record of women's experience of these will be collected at each monthly visit.

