# 12.1 **DEFINITIONS**

An **adverse event** (AE) is any untoward medical occurrence in a clinical trial participant which does not necessarily have a causal relationship with an investigational medicinal product (IMP).

An **adverse reaction** (AR) is any untoward and unintended response to an IMP which is related to any dose administered to that participant.

A serious adverse event (SAE), serious adverse reaction (SAR). Any AE or AR that at any dose:

• results in death of the clinical trial participant – including neonatal deaths\*\*

- is life threatening\*;
- adverse medicine experience
- requires in-patient hospitalisation^ or prolongation of existing hospitalisation;
- results in persistent or significant disability or incapacity\*\*
- congenital anomaly/birth defect or spontaneous abortion (miscarriage)
- cancer new onset or recurrent \*\*
- Immune Dysfunction: new diagnosis either of HIV or life-threatening immunodeficiency diseases.
- An important medical event, based on appropriate medical judgment that jeopardises the participant and may require intervention to prevent one of the outcomes listed above.

\*Life-threatening in the definition of an SAE or SAR refers to an event where the participant was at risk of death at the time of the event. It does not refer to an event which hypothetically might have caused death if it were more severe.

\*\* Reportable events regardless of the relationship to the IMP.

^Any hospitalisation that was planned prior to enrolment (such as hospitalisation for delivery of the baby) will not meet SAE criteria. Any hospitalisation that is planned post enrolment will meet the SAE criteria.

A suspected unexpected serious adverse reaction (SUSAR) is any AR that is classified as serious and is suspected to be related to the IMP contained in the Reference Safety Information (RSI) for that IMP. The RSI is contained in the Summary of Product Characteristics (SPC) for the IMP, which was submitted to the PMPB as part of the approvals process. The RSI is usually comprised of the 'undesirable effects' detailed in section 4.8 of the SPC; this section is used to assess the expectedness of an SAR.

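### Section 12.5.2 confines AEs and SAEs to events judged unrelated to the drug, contradicting section 12.1 and leaving the adverse-event endpoint open to two different counts

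*Protocol*

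**What the plan says.** Section 12.5.2 gives four causality grades: definitely, probably or possibly related, and not related. An event in any of the first three "will be deemed an AR or SAR (and, if unexpected, a potential SUSAR) for onward reporting purposes". The next sentence reads: "Only events that are considered to be 'Not Related' to the IMP will be deemed AEs or SAEs".

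Section 12.1 defines an adverse event as "any untoward medical occurrence in a clinical trial participant which does not necessarily have a causal relationship with an investigational medicinal product".

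The secondary endpoints in the Trial Summary include "Adverse events in each group". Section 11.2 plans a mean (SD) or incidence for secondary outcomes, overall and by arm, with no formal comparison between arms.

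**The concern.** The word 'Only' makes the two pairs of labels mutually exclusive: an event judged related is an AR or SAR and is no longer an AE or SAE. Under section 12.1 an adverse reaction is one kind of adverse event, so the two sections cannot both be followed.

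This reaches an endpoint because the endpoint is worded with the very term that the two sections define differently. It is the one listed endpoint devoted to adverse events, and a feasibility trial of metformin needs it to show tolerability. Section 12.4 has every event assessed as though the woman were taking metformin. It is therefore reasonable to expect, though the protocol does not say so, that the gastrointestinal symptoms named in section 9.1 would often be judged at least possibly related in both arms. A table restricted to unrelated events would be weakest where the information is most wanted.

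**Working it through.** No arithmetic applies: the protocol gives no adverse-event rate and no expected share of events judged related. The check has two steps.

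**Step 1. How the protocol uses the terms elsewhere.**

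| Place | Use of the term | Fits 12.1? | Fits the 12.5.2 sentence? |
|---|---|---|---|
| 9.1 | The commonest metformin reactions are to be "reported as AE's any of these symptoms that have been experienced during the seven day period" before the visit, with no causality filter | Yes | No, for any judged related |
| 12, opening text | A recording rule begins: "In the case of a common AE (known to be caused by Metformin and documented in the SPC" | Yes | No: an event caused by the drug is called an AE |
| 12.2 | A listed pregnancy event thought possibly related is to be submitted as an SAE | Yes | No: it would be a SAR only |
| 12.4 | Each AE is assessed for causality | Yes | No: causality would have to be settled before the event could be called an AE |
| 12.5.2, preceding sentence | Its subject is an AE or SAE that is considered related | Yes | No: the two adjacent sentences disagree |

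One sentence stands against the definition and against each of these uses.

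**Step 2. What would follow if the sentence were applied.** Sort events by causality and seriousness, and take the endpoint to include serious as well as non-serious AEs. Section 12.5.4 asks for a severity rating of AEs, SAEs, SARs and SUSARs, and does not list ARs. Section 12.5.1 assigns toxicity grades to all SAEs, and does not list SARs.

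| Event | Label under 12.1 | Label under the 12.5.2 sentence | Counted in the endpoint under 12.5.2? | Severity (12.5.4) under 12.5.2? | Toxicity grade (12.5.1) under 12.5.2? |
|---|---|---|---|---|---|
| Not related, not serious | AE | AE | Yes | Yes | Not required |
| Not related, serious | AE and SAE | SAE | Yes | Yes | Yes |
| Related, not serious | AE and AR | AR | **No** | **No** | Not required |
| Related, serious | AE, SAE, AR and SAR | SAR | **No** | Yes | **No** |

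Under section 12.1 all four kinds count towards the endpoint, all are rated for severity, and both serious kinds receive a toxicity grade. Under the 12.5.2 sentence the two related kinds leave the endpoint, non-serious related events are not listed for severity, and serious related events are not listed for a toxicity grade.

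**The case against.** The strongest reply is that the sentence concerns pharmacovigilance routing only. The sentence before it relabels related events for onward reporting, and no part of the protocol ties the endpoint to that label. Section 9.1 separately has the common metformin symptoms reported as AEs whatever their cause. Section 12.3 records causality with each event, so an all-cause table with a related subset can be built from the data however events are labelled. Counting rules can also be left to the statistical analysis plan, which section 11.2 promises before unblinding.

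Much of this stands. It shows that related events are not lost from capture and that the endpoint need not be counted by the 12.5.2 label. It does not remove the contradiction. The limiting phrase belongs to the preceding sentence, and the disputed sentence carries no such limit. Nothing gives section 12.1 or 9.1 precedence over 12.5.2, so an event could be entered as an AE under 9.1 and relabelled an AR once causality is judged. Nor is this a detail left for the analysis plan: it is a rule that the protocol states wrongly, and a plan written from this protocol would inherit both definitions.

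**Conclusion.** The contradiction is real and worth correcting. The protocol defines an adverse event in two incompatible ways, and one of them, if used for counting, would take suspected drug-related events out of the by-arm adverse-event endpoint and out of two grading rules. The conclusion rests on the wording alone. Whether any loss occurs depends on which definition the analysis follows, and its size cannot be derived from the documents.

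Two stronger readings are tempting, and the documents support neither. A reader might infer that the endpoint, as planned, drops every event suspected to be caused by metformin. No passage says that the endpoint uses the 12.5.2 label, and sections 12.1 and 9.1 point the other way. A reader might also infer that serious related events would go unreported. But the title of section 12.6 covers SARs and SUSARs as well as SAEs, section 12.2 sends possibly related listed events in as SAEs, and the annual report in section 12.7 lists SARs and SUSARs. The fault is one of labelling and counting, not of missing data.

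**What to change.** Replace the last sentence of that paragraph in section 12.5.2 with wording such as: *All untoward events are AEs (SAEs if serious) irrespective of causality; those judged definitely, probably or possibly related are additionally classified as ARs/SARs for onward reporting.* With that wording the lists in sections 12.5.1 and 12.5.4 cover related events without further change.

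Also state that the Trial Summary endpoint counts all AEs and SAEs whatever their causality, by arm, with related events shown as a subset. The endpoint is missing from the list in section 2.2.2. That is a separate and minor discrepancy, but it can be put right in the same amendment.

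The cost is one reworded sentence and one clarifying sentence. Sections 12.3 and 12.4 already require causality and seriousness to be assessed for each event, so no new data are needed.

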# 12.5.3 Assessment of Expectedness

If the event is an AE the evaluation of expectedness will be made based on knowledge of the reaction and the relevant Reference Safety Information (RSI) information documented in the SPC.

The event may be classed as either:

- **Expected**: the AE is consistent with the undesirable effects of the IMP listed in the RSI (section 4.8 of the SPC).
- **Unexpected**: the AE is not consistent with the known undesirable effects detailed in the RSI

#### 12.5.4 Assessment of Severity

The Investigator will make an assessment of severity for each AE/SAE/SAR/SUSAR and record this on the ECRF/AE log or SAE form according to one of the following categories:

- **Mild**: an event that is easily tolerated by the participant, causing minimal discomfort and not interfering with every day activities.
- **Moderate**: an event that is sufficiently discomforting to interfere with normal everyday activities.
- Severe: an event that prevents normal everyday activities.

Note: the term 'severe', used to describe the intensity, should not be confused with 'serious' which is a regulatory definition based on participant/event outcome or action criteria. For example, a headache may be severe but not serious, while a minor stroke is serious but may not be severe.

#### 12.6 REPORTING OF SAEs/SARs/SUSARs

Once the Investigator becomes aware that an SAE has occurred in a study participant, the information will be reported to the PMPB and Sponsor's office **within 24-48 hours of site awareness**. The information will be input, via a tablet device, into the safety reporting page of the same electronic interface used for the eCRF. If the Investigator does not have all information regarding an SAE, they should not wait for this additional information before notifying the authorities and Sponsors. The SAE report can be updated later when the additional information is received.

The SAE form will be printed and transmitted to the PMPB board by fax or hand delivered to:

The Registrar Pharmacy, Medicines and Poisons Board [name] [contact]

#### And a scanned copy sent via email to [contact]

Only forms in a pdf format will be accepted by Sponsors via email. Forms may also be sent by fax on **[contact]** Where missing information has not been sent to the Sponsors will contact the Investigator and request that the missing information is provided via the tablet device interface. The Investigator must respond to these requests in a timely manner.

All reports submitted faxed to the PMPB and Sponsors including any follow up information will be retained by the Investigator in the Investigator Site File (ISF) including all acknowledgements of receipt.

# 12.7 REGULATORY REPORTING REQUIREMENTS

The Sponsor is responsible for pharmacovigilance reporting and has a legal responsibility to notify the regulatory competent authority (PMPB), the relevant ethics committees RECs that approved the trial and Merck KGaA as the provider of the IMP. Fatal or life threatening SUSARs will be reported to the RECs no later than 7 calendar days, and all other SUSARs will be reported no later than 15 calendar days, after the Sponsor is first aware of the reaction.

The Sponsor (or delegate) will inform Investigators at participating sites of all potential SUSARs and any other arising safety information.

The Sponsor will be responsible for providing safety line listings and assistance; however, it is the responsibility of the Chief Investigator to prepare the Development Safety Update Report. This annual report lists all SARs and SUSARs reported during that time period. The responsibility of submitting the Development Safety Update Report to the regulatory authority and RECs, lies with the sponsor.

#### 12.8 FOLLOW UP PROCEDURES

After initially recording an AE or recording and reporting an SAE, the Investigator should make every effort to follow each event until a final outcome can be recorded or reported as necessary. Follow up information on an SAE will be reported to the PMPB and the Sponsors office, via the tablet device interface.

If, after follow up, resolution of an event cannot be established, an explanation should be recorded on the eCRF or SAE log or additional information section of SAE form.

# 13. TRIAL MANAGEMENT AND OVERSIGHT ARRANGEMENTS

### 13.1 TRIAL MANAGEMENT GROUP

The trial will be coordinated by a Trial Management Group (TMG), consisting of the grant holders (Chief Investigator and Principal Investigator in Edinburgh), Trial collaborators and Trial Manager.

The Trial Manager will oversee the study and will be accountable to the Chief Investigator. The Trial Manager will be responsible for reviewing the eCRF for completeness, plausibility and consistency. Any queries will be resolved by the Investigator or delegated member of the trial team.

A Delegation Log will be prepared for each site, detailing the responsibilities of each member of staff working on the trial.

#### **13.2 TRIAL STEERING COMMITTEE**

A Trial Steering Committee (TSC) will be established to oversee the conduct and progress of the trial. The terms of reference of the Trial Steering Committee, the draft template for reporting and the names and contact details are detailed in the DSMC & TSC Charters.

#### 13.3 INDEPENDENT DATA SAFETY AND MONITORING COMMITTEE

An independent Data Safety and Monitoring Committee (iDSMC) will be established to oversee the safety of participants in the trial. The iDSMC is established to protect and serve the study participants, in particular with regard to safety and to assist and advise Investigators and the Trial Steering Committee, so as to protect the validity and credibility of the trial. To safeguard the interests of trial participants, assess the safety and efficacy of the interventions during the trial, and monitor the overall conduct of the clinical trial. The terms of reference of the Data Monitoring Committee and the names and contact details are detailed in the iDSMC Charter.

The iDSMC will consist of both local and international members with a broad range of clinical, experience. The iDSMC members are independent of the trial (that is, they are not involved with the Study trial in any other way or have some competing interest that could impact on the PAPAGENO trial). Any competing interests, both real and potential, must be declared.

The iDSMC Charter will be signed by the appropriate individuals preferably prior to the trial commencing.

### 13.4 INSPECTION OF RECORDS

Investigators and institutions involved in the study will permit trial related monitoring and audits on behalf of the sponsor, REC review, and regulatory inspection(s). In the event of an audit or monitoring, the Investigator agrees to allow the representatives of the sponsor direct access to all study records and source documentation. In the event of regulatory inspection, the Investigator agrees to allow inspectors direct access to all study records and source documentation.

#### 13.5 RISK ASSESSMENT

A study specific risk assessment will be performed by representatives of the sponsor monitors and the QA group, in accordance with the sponsor's governance and sponsorship SOPs. Input will be sought from the Chief Investigator or designee. The outcomes of the risk assessment will form the basis of the monitoring plans and audit plans. The risk assessment outcomes will also indicate which risk adaptions could be incorporated into to trial design.

# 13.6 STUDY MONITORING AND AUDIT

The sponsor, clinical trial monitors, or designees, will perform monitoring activities in accordance with the study monitoring plan. This will involve remote monitoring activities as far as is practical and some onsite monitoring as necessary. The Sponsor's QA personnel, or designees, will perform study audits in accordance with the study audit plan. This will involve investigator site audits, study management audits and facility (including 3rd parties) audits as necessary.

#### 14. GOOD CLINICAL PRACTICE

#### 14.1 ETHICAL CONDUCT

The study will be conducted in accordance with the principles of the International Conference on Harmonisation Tripartite Guideline for Good Clinical Practice (ICH GCP).

Before the study can commence, all required approvals will be obtained and any conditions of approvals will be met.

# 14.2 REGULATORY COMPLIANCE

The study will not commence until a Clinical Trial Authorisation (CTA) is obtained from the appropriate Regulatory Authority. The protocol and study conduct will comply with the Medicines for Human Use (Clinical Trials) Regulations 2004 in the UK and the Pharmacy, Medicines and Poisons Act (PMPA) (January 15, 1991) Ministry of Health, as amended.

# 14.3 INVESTIGATOR RESPONSIBILITIES

The Principal Investigator (PI) is responsible for the overall conduct of the study at the site and compliance with the protocol and any protocol amendments. In accordance with the principles of ICH GCP. Responsibilities may be delegated to an appropriate member of study site staff.

Delegated tasks must be documented on a Delegation Log and signed by all those named on the list prior to undertaking applicable study-related procedures.

#### 14.3.1 Informed Consent

The PI is responsible for ensuring informed consent is obtained before any study specific procedures are carried out. The decision of a participant to participate in clinical research is voluntary and should be based on a clear understanding of what is involved.

Potential Participants must receive adequate oral and written information – appropriate Participant Information and Informed Consent Forms will be provided. The oral explanation to the woman will be performed by the Investigator or qualified delegated person, and must cover all the elements specified in the Participant Information Sheet and Consent Form.

The participant must be given every opportunity to clarify any points they do not understand and, if necessary, ask for more information. The participant must be given sufficient time to consider the information provided. It should be emphasised that the participant may withdraw their consent to participate at any time without loss of benefits to which they otherwise would be entitled.

The participant will be informed and agree to their medical records being inspected by regulatory authorities and representatives of the sponsor(s).

The Investigator or delegated member of the trial team and the participant will sign and date the Informed Consent Form(s) to confirm that consent has been obtained. The original will be signed in the Investigator Site File (ISF). The participant will receive a copy of the signed consent form.

If a woman is unable to read an impartial witness should be present during the entire informed consent discussion. If capable of doing so, the woman should sign and date the form; then the independent witness should sign and personally date the consent form.

NB An impartial witness may be:

- 1. A relative/friend of choice accompanying the woman to the appointment
- 2. A Member of staff at the site, not involved in the trial (for example support staff)
- 3. Another participant/ patient in hospital who is literate, and is willing to stand in as witness and is accepted by the prospective participant.

The witness should be made aware that they are confirming that the trial has been accurately explained, appeared to be understood and consent was freely given.

